10.4.1 Supervised classification and correlation

Using the insights gleaned from visualizing the data, the expert clinician group will lead the generation of clinically supervised modifications to the static algorithms in ePOCT+ that aim to 1) reduce resource consumption (e.g. predicting the results of expensive or unavailable

diagnostic tests), 2) improve or personalize diagnostic accuracy (e.g. creating algorithms adapted to local epidemiology, or better identifying patients who had severe outcomes in phase 1) or 3) improve the completeness of data collected by asking questions that would better predict the values that are missing. For this, the algorithm building platform will allow clinicians to explore various predictive methods, ranging from logistic regression, neural networks and random forests. They will control the inputs required to make the prediction and decide at what threshold the predicted result will impact care decisions. The algorithm will then be updated with accumulating data to best reflect its dynamic environment.

10.4.2 Anomaly detection

Various methods allow us to identify and visualize clusters of abnormal data, by highlighting these instances, clinicians and epidemiologists can train the algorithms by labeling which are of interest and what, if any, actions should be taken when they are detected. Various methods will be explored for this aim and adapted to the type of anomaly under investigation (for example unsupervised density-based approaches such as isolation forests, and k-nearest neighbors [KNN] or multidimensional non-linear kernel-based techniques such as self-organizing maps [SOM] and support vector clustering [SVC]). The clusters deemed interesting will then be investigated for gold-standard labeling by clinicians and the surveillance team and visualizations may be exported to users of the tool for training purposes (medAL-monitor).

10.5 Analyses of data from operational research studies

Quantitative data from cross-sectional quality of care surveys, provider clinical competency or knowledge assessments, and caregiver and patient interviews will be analyzed using conventional statistical methods to compare means (t-tests or paired t-tests) or frequencies (chi-square tests) across intervention groups or time periods. Regression analysis may also be used to explore associations of multiple predictors with outcomes of interest.

All interviews and focus-group discussions will be audio-recorded with the participant's informed consent. Detailed notes will be taken during the interviews. Records will be manually transcribed in its original language (Kiswahili) and translated into English. A qualitative data analysis software (e.g. Nvivo) will be used to code the English interview transcripts in order to identify emerging themes. A predefined list of codes based on the interview guide and the recurrent themes highlighted in the detailed notes will be used. New codes will be created when new themes are identified during more detailed analysis of the transcripts. Deductive coding will be used to extract the themes based on the interview guide, but inductive coding will also be used to extract any unexpected themes that arise during the interviews.

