	Syndromic surveillance enhanced by microbiological testing: Syndromic surveillance (i.e. based on the clinical data generated by the use of
	Three cross-sectional surveys in a subset of randomly selected HFs will be performed to assess the quality of the consultation done by HCWs and their level of compliance with the algorithm. Among the 40 HFs included in Phase 1, 18 (10 in Morogoro and 8 in Mbeya, half interventions and half controls) will be randomly selected. 25 consultations per HF will be observed for a total 450 HCW/child pairs. The survey will be performed once before the start of the study, once during Phase 1 and again approximately 6 months later during Phase 2 in the same facilities, with the aims of assessing changes in the use of ePOCT+ over time in the initial intervention facilities and a before-and-after ePOCT+ analysis in the initial control facilities.
	Cross-sectional quality of care surveys:
	Examples of algorithm modifications expected to have a positive impact that will be explored for implementation are: 1) adapting the frequency of malaria testing in areas with very low endemicity; 2) improving the accuracy of pneumonia diagnosis; 3) assessing the utility of using dengue rapid tests if an outbreak occurs; 4) or typhoid rapid tests in areas of high prevalence; 5) improving the prediction of severe disease; 6) improving the algorithm for children with chronic conditions (malnutrition, HIV or sickle-cell). Other type of changes might also be tested if considered important by the clinical experts.

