Primary outcome measures: (i) For assessing clinical cure at Day 7, a simple questionnaire (asking if the child is still sick, was hospitalized secondarily, or died) will be administered to all caregivers by phone; (ii) For measuring antibiotics prescribed at initial consultation, the treatment data recorded in the tablets or PCs by HCWs throughout the study will be compared between intervention and control arms.

Secondary outcome measures: To determine the quality of the consultation made by CHWs, including the rational use of antimicrobials (antibiotics and antimalarials), two sources of data will be used and compared between intervention and control arms:

- the final decision on referral, tests performed, final diagnoses retained and treatment prescribed will be recorded in the tablets or PCs by HCWs at initial consultations and re-attendance visits.

- during a cross-sectional survey, observers in the consultation room will record key symptoms and signs assessed by HCWs, diagnostic tests requested, final decision on referral, final diagnoses retained and treatment prescribed.

Control arm: In control PHC facilities, sick children will be assessed, diagnosed and treated as per routine protocols by clinicians. A similar but simplified tablet or PC application will also be used in control facilities, but only to record outcome measure related data using an electronic case report form. HCWs in control facilities will be offered the usual training and supervision proposed by the CHMT.

In **Phase 2**, all selected HFs in the two regions will receive the intervention. Indicators monitored over time and across geographical areas will be measured the same way as in Phase 1, except that clinical cure, secondary hospitalizations and deaths will be assessed through an automated SMS sent to caregivers (rather than a phone call) using the same simple questionnaire.

Objective 2: Improve the algorithm and adapt it to spatiotemporal variations

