3.4.1 Cross-sectional quality of care surveys

Before the start of phase 1, during the second half of phase 1, and around 6 months after the beginning of phase 2, three cross-sectional surveys in a subset of randomly selected HFs will be performed to assess the quality of the consultation done by HCWs and their level of compliance to the algorithm (and thus to guidelines). Among the 40 HFs included in Phase 1, 18 HFs (10 in Morogoro and 8 in Mbeya, half of them being intervention HFs and the other half control HFs) will be randomly selected. Observers will be trained to attend and observe (without interfering) 25 consecutive consultations with children aged 1 day to 14 years per HF, thus a total 450 HCW/child pairs. Changes over time will be assessed during the three cross-sectional surveys. Before-and-after intervention analysis will be performed between the baseline analysis and the phase 1 intervention arm HFs, as well as between the control arm HFs in phase 1 and those same HFs that will then use the ePOCT+ tool in Phase 2. For the9 intervention HFs, this will provide another way (besides data recorded through the ePOCT+ tool) to measure potential improvement in the quality of the consultation over time. The tools for the quality of care surveys can be found in **Appendix 1**.

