These measures or indicators include the evaluation of the effects of the use of ePOCT+ (versus routine care in Phase 1; over time and across geographical areas in Phase 2) for managing sick children aged under 14 years presenting to PHC facilities on:

Unscheduled secondary consultations:

- % of children with one or more unscheduled re-attendance visits at any HF by day 7 *Severe outcome by day 7:*

- % of children with non-referred secondary hospitalization by day 7
- % of children who have died by day 7

Primary referrals:

- % of children referred to hospital or admitted to inpatient ward at a health centre at initial consultation
- % of children who were hospitalized among those referred (i.e. referral completed)

Appropriate case management for malaria at initial consultation

- % of febrile children tested for malaria
- % of malaria positive children prescribed an antimalarial
- % of malaria negative children prescribed an antimalarial
- % of untested children prescribed an antimalarial

Appropriate case management for other conditions at initial consultation

- % of key symptoms and signs checked and diagnostic tests performed by HCWs
- Distribution of final diagnoses (including their severity) made by HCWs
- Concordance between treatment prescribed and final diagnoses made by HCWs
- Concordance between final diagnoses as proposed by ePOCT+ and final diagnoses by HCW *(intervention HFs only)*

Definitions used for the outcome measures and indicators of objective 1

- Clinical cure is a positive answer to the question "Is the child cured?" OR "Has the child improved?" (if not cured) asked to caregiver through a phone call (or home visit) at day 7. Non-referred secondary hospitalizations (see definition below) will however be considered as clinical failures even if the child is already cured at day 7.
- Initial consultation is the first visit of a sick child for an acute problem at a HF participating in the study (and thus registered electronically); timeframe from completion of the initial visit up to midnight of the same day.
- Re-attendance visit is a consultation (not necessarily at a HF participating in the study) taking place from the day after initial consultation up to day 7 included. A re-attendance visit can be scheduled (proposed by the HCW on a certain day) or unscheduled (upon decision by caregivers).

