Analyses will follow CONSORT guidelines (Schulz et al. 2010, Piaggio et al. 2012) and intention-totreat (ITT) principles, that is including all participants as randomized. A flowchart will describe the inclusion and follow-up of participants by study arm. Baseline characteristics will be described by study arm with summary statistics such as median and interquartile range or number and percentage; no formal testing between arms will be performed (Pocock et al. 2002). Outcomes will be described by arm using summary statistics. For the non-inferiority comparison between ePOCT+ and the control arm for clinical cure, a CI approach will be used. A figure illustrating the CIs and the non-inferiority margin will be presented. Primary analyses for the non-inferiority comparison will be performed on both the per protocol and ITT sets (Committee for Proprietary Medicinal P 2001). If ePOCT+ is found to be non-inferior to the control in terms of clinical cure rate, then we will assess for superiority using the ITT set. If non-inferiority is established, we will test for significant differences in the co-primary outcome of antibiotic prescription rate. For this outcome, the percentage of patients receiving antibiotics at day 0 will be assessed using multi-level logistic regression model regression with the cluster included as a random effect. Binary secondary outcomes will be evaluated in the same way. All estimates will be reported with 95% confidence intervals (CI).

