Effect modification of the primary outcome of antibiotic prescription of the primary endpoints will be performed in groups of patients where the highest reduction in antibiotic prescription is expected, and areas of extension of the content of the algorithm compared to the version tested in the previous ePOCT study. Effect modification by sex, age groups (young infants ages 1 to 59 days, children aged 2 months to 5 years, and children aged 5 to 14 years), respiratory symptoms, fever without clinical source, gastrointestinal complaints (vomiting and diarrhea), skin problems, ear and throat problems, anemia, and malnutrition will be assessed by incorporating an interaction between arm and the respective variable, acknowledging that power will be low. All models will be adjusted for clustering and the stratification factors (Kahan et al. 2012). Primary analyses will be complete case; we may adjust for further baseline variables which are associated with missing outcome data (which is analogous to performing multiple imputation in the case of a single endpoint). Further details will be provided in the statistical analysis plan.

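### Protocol 10.5 tests the quality-of-care surveys with t-tests and chi-square tests and makes no allowance for facility clustering

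*Protocol*

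**What the plan says.** Protocol 3.4.1 draws "18 HFs (10 in Morogoro and 8 in Mbeya, half of them being intervention HFs and the other half control HFs"), and observes "25 consecutive consultations with children aged 1 day to 14 years per HF, thus a total 450 HCW/child pairs" in each of three rounds. Two kinds of contrast are planned. One is between arms: the Synopsis (Procedures and measurements, Objective 1) names the tablet records and the survey as sources for the secondary outcomes and says that "two sources of data will be used and compared between intervention and control arms". The other is over time in the same facilities, including "a before-and-after ePOCT+ analysis in the initial control facilities" (Synopsis, Study design).

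Protocol 10.5 says these data will be used to "compare means (t-tests or paired t-tests) or frequencies (chi-square tests) across intervention groups or time periods", with regression as an optional exploratory extra. It names no facility effect, robust variance, design effect or facility-level summary.

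Protocol 10.3 handles the trial outcomes differently. It puts a cluster random effect in the antibiotic model, then states: "Binary secondary outcomes will be evaluated in the same way" and "All models will be adjusted for clustering and the stratification factors". Protocol 7.1 lists among the secondary measures the percentage "of key symptoms and signs checked and diagnostic tests performed by HCWs". The secondary outcome list in SAP 6.1.2 omits that item, and the SAP has no survey analysis.

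**The concern.** Consultations in one facility share staff, supplies and habits. Protocol 3.1 justifies randomizing facilities on the ground that the facility context shapes how clinicians practise, so some within-facility correlation is to be expected in practice items. A test that pools 225 consultations per arm as if independent understates the standard error of the arm difference.

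The plan also points two ways. A binary survey measure that serves as a secondary outcome falls under the cluster model of 10.3 and under the simple tests of 10.5. Any other survey measure has only 10.5.

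For symptoms and signs checked, the survey is the only between-arm source. Under Protocol 8.1.7 the control tablets hold demographics and end-of-consultation decisions, and SAP 5.4 says clinical signs are not systematically collected. A false positive on this item could not be checked against tablet data.

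**Working it through.** **Inputs.** Protocol 3.4.1 gives 18 facilities and 25 consultations each: 18 × 25 = 450, which matches the stated total. With half the facilities in each arm, that is 9 facilities and 9 × 25 = 225 consultations per arm. The documents give no power, alpha or ICC for the surveys. A two-sided 5% test is assumed. The only ICC, 0.002, is for the day-7 clinical outcome (Protocol 10.1.1); 0.02, 0.05 and 0.10 are assumptions.

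**Between arms.** Let V be the true variance of the arm difference divided by the variance that a consultation-level test uses, and f the share of facility variance explained by region, with arms balanced within region:

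V = 1 − ICC + 25 × ICC × (1 − f); type I error = 2 × [1 − Φ(1.96/√V)]

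For example, at ICC 0.02 and f = 0: V = 1 − 0.02 + 0.50 = 1.48, 1.96/√1.48 = 1.61, error 10.7%.

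| ICC | V, f = 0 | Type I error | V, f = 0.5 | Type I error |
|---|---|---|---|---|
| 0.002 | 1.048 | 5.6% | 1.023 | 5.3% |
| 0.02 | 1.48 | 10.7% | 1.23 | 7.7% |
| 0.05 | 2.20 | 18.6% | 1.575 | 11.8% |
| 0.10 | 3.40 | 28.8% | 2.15 | 18.1% |

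The error passes 10% at an ICC of about 0.0175 (f = 0) or 0.0365 (f = 0.5).

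**Simulation.** Beta-binomial data were generated with a true proportion of 50% and 25 consultations per facility, 5 v 5 facilities in Morogoro and 4 v 4 in Mbeya (40,000 runs). Type I error at ICC 0.002, 0.02, 0.05 and 0.10:

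| Test | f | 0.002 | 0.02 | 0.05 | 0.10 |
|---|---|---|---|---|---|
| Chi-square, uncorrected | 0 | 5.7% | 11.2% | 19.2% | 29.7% |
| Chi-square, uncorrected | 0.5 | 5.6% | 8.2% | 12.3% | 18.5% |
| Chi-square, continuity-corrected | 0 | 4.6% | 9.5% | 17.0% | 27.4% |
| Chi-square, continuity-corrected | 0.5 | 4.6% | 6.9% | 10.6% | 16.6% |

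So with the continuity correction there is no inflation at ICC 0.002. Analysing the 18 facility means with adjustment for region (15 df) gave 4.9% to 5.2% in all eight combinations of ICC and f. A plain t-test on facility means (16 df) also held about 5% at f = 0. At f = 0.5 it became conservative (4.7%, 3.2%, 2.2%, 1.4%), which is why region should be in the model.

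**Before-after, same facilities, consultations unpaired.** With r the correlation of a facility's effect between rounds, V = 1 − ICC + 25 × ICC × (1 − r).

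| ICC | r = 1 | r = 0.8 | r = 0.5 | r = 0 |
|---|---|---|---|---|
| 0.02 | 4.8% | 5.9% | 7.7% | 10.7% |
| 0.10 | 3.9% | 9.8% | 18.1% | 28.8% |

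The problem is smaller than between arms for any positive r, and the same size at r = 0.

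**The case against.** - **The unit of analysis is unstated.** Section 10.5 does not say consultations are the unit. A t-test on facility means would be valid, and a paired t-test across rounds could only pair facilities or health workers, because each round observes different children. This stands for means, and it is why the error rates above are conditional. It does not rescue the chi-square tests, which ordinarily count consultations, and pairing cannot cover the between-arm contrasts. The mention of paired tests may in any case refer to the training pre- and post-tests.
- **Section 10.3 may already govern.** On this reading 10.3 covers formal trial outcomes and 10.5 is a general paragraph for operational research. This stands in part, for binary survey measures that are secondary outcomes. No text says that 10.3 prevails, the SAP is silent, and other survey measures are outside 10.3.
- **The size rests on assumed ICCs.** This stands. At the one documented ICC the inflation is about half a point or none. The documents support the existence of correlation in practice items, not its size.
- **The regional figures need balance within region.** This stands. Protocol 3.4.1 says half of the facilities are intervention, but not that this holds in each region.
- **It is not a primary analysis.** This stands, and it limits the weight of the point.

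**Conclusion.** The concern holds. Followed as written, with consultations as the unit, 10.5 gives between-arm survey tests that reject too often: about 5.6% at ICC 0.002, and about 11% to 29% at assumed ICCs of 0.02 to 0.10 (8% to 18% if half the facility variance is regional and arms are balanced by region). The before-after contrasts are affected less as long as facility effects correlate positively between rounds; with full persistence the tests are slightly conservative. The direction follows from the design, but the size depends on ICCs the documents do not give. It should be corrected before the survey data are analysed. The co-primary analyses and the rule for declaring the study a success do not depend on it.

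**What to change.** Amend Protocol 10.5 as follows.

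- **Between arms:** a model with a facility random effect and small-sample degrees of freedom, or an analysis of facility-level summaries. Adjust for the stratification factors where feasible, and at least for region; 18 facilities cannot carry council, facility type and attendance together. Facility means with region leave 15 df.
- **Before-after:** paired facility-level differences (9 facilities, 8 df) or an equivalent mixed model.
- **SAP:** state whether the survey item is a secondary outcome and that this cluster-adjusted method governs it.

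The cost is wording and usually wider intervals; the data are the same. For a binary item at 50%, the 95% half-width is t × √(0.5 × V/225), with t = 2.131 (15 df) or 2.306 (8 df). The consultation-level figure is 1.96 × √(0.5/225) = 9.2 points.

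| Between arms, percentage points | ICC 0.002 | 0.02 | 0.05 | 0.10 |
|---|---|---|---|---|
| Half-width, f = 0 | 10.3 | 12.2 | 14.9 | 18.5 |
| Half-width, f = 0.5 | 10.2 | 11.1 | 12.6 | 14.7 |
| Detectable with 80% power, f = 0 | 14 | 17 | 21 | 26 |
| Detectable with 80% power, f = 0.5 | 14 | 16 | 18 | 21 |

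Before-after half-widths at ICC 0.10 become 10.3, 12.9 and 15.9 points for r = 1, 0.8 and 0.5. Under these assumptions, this is the precision that 9 facilities per group can support.

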11 INFORMATION TECHNOLOGY, DATA MANAGEMENT AND MONITORING

11.1 Overall IT solution

The overall IT solution is provided by several components; some of them have been already discussed or presented previously, the diagram (**Figure 10**) below is the complete overview of the solution. From left to right we have the following components:

MedAL-Creator: The clinical algorithm management system that will allow to manage, reference, modify and deploy the different versions of the algorithm into a mobile device. MedAL-Creator is hosted in Switzerland and managed by the IT Unisanté team.

ePOCT+: The application (tablet or PC) that will contain the algorithm and be used for data acquisition by the HCW. The ePOCT+ could be deployed in a standalone or multi-device mode. In a standalone mode the application will receive updates of the algorithm directly from MedAL-Creator.

Local Data: The application that enables ePOCT+ to work in a multi-device environment. It plays a role of central database at the HF level. This software will receive the updates of the algorithm from MedAL-Creator.

Data Management System: this component will be considered as the data hub of our solution. Hosted on a server at the Dar es Salaam head office of IHI:

- Main Data: This is the data collector for the country, it plays several roles:
 - Data collector
 - Data manager (Clean, Quality Check, Audit trail, Anonymization)
 - Data publisher
 - Data monitoring
- medAL-outbreak: Indicators for disease surveillance and early epidemic warning and response will be decided with and provided to CHMTs through a dedicated web-based application
- medAL-monitor: Targeted supervision to HFs by the CHMT will be organized based on the quality of care indicators calculated in real time from the uploaded data and made available through a web-based dashboard
- Research Database: This is a database only with anonymized data where the machine learning team will do their analyses.

[figure not shown]

[figure not shown]
Figure 10: IT architecture.

11.2 Data flow

The data flow is shown in **Figure 11**. Data collection starts at the HF where the study clinicians capture the data using ePOCT+. When an Internet connection is available ePOCT+ (or Local Data in multi-devices set-up) will sync the data with the data management system hosted at IHI. The data management team at IHI will monitor, clean and anonymize the data in this system and make the anonymized data available for the Unisanté IT team. The Unisanté IT team will monitor the data received, communicate the possible errors or anomalies before sending them to the EPFL ML team for ML-based statistics.

Figure 11: Data flow.

